## **10.1 Analysis sets**

### **10.1.1 Full Analysis Set**

The Full Analysis Set (FAS) comprises all patients who received at least one dose (partial or complete) of everolimus. The FAS will be used for all listings of raw data.

### **10.1.2 Safety Set**

The Safety Set includes all patients who received at least one dose (partial or complete) of everolimus, and have at least one valid post-baseline safety assessment. The statement that a patient had no AEs (on the AEs CRF) constitutes a valid safety assessment.

## **10.2 Patient demographics/other baseline characteristics**

Patient demographics and baseline characteristics will be listed by patient.

## **10.3 Treatments (study treatment, concomitant therapies, compliance)**

Everolimus dose administration will be listed by patient.

## **10.4 Primary objective**

Primary objective of this trial is to collect and assess the long-term safety everolimus in patients who are currently receiving treatment in the parent study and who are benefiting from treatment with everolimus.

### **10.4.1 Analysis set and grouping for the analyses**

For all safety analyses, the safety set will be used.

The overall observation period will be divided into two mutually exclusive segments:

1. on-treatment period: from day of first dose of study medication to 30 days after last dose of study medication
2. post-treatment period: starting at day 30 after last dose of study medication.

### **10.4.2 Adverse events (AEs)**

Summary tables for AEs have to include only AEs that started or worsened during the on-treatment period, the **treatment-emergent** AEs. However, all safety data (including those from the post-treatment periods) will be listed and those collected during the post-treatment period are to be flagged.

The incidence of AEs (new or worsening from baseline) will be summarized by system organ class and preferred term, severity (based on CTCAE grades), type of AE and relation to study treatment.

Deaths reportable as SAEs and non-fatal serious AEs will be listed by patient.

Specific safety event categories will be considered. Such categories consist of one or more well-defined safety events which are similar in nature and for which there is a specific clinical interest in connection with the study treatment(s).

## **10.5 Sample size calculation**

No formal sample size calculation is required for this trial since only patients who are still on treatment in the parent study will be enrolled in this trial.

# **11 Ethical considerations and administrative procedures**

## **11.1 Regulatory and ethical compliance**

This clinical study was designed, shall be implemented and reported in accordance with the International Conference on Harmonization (ICH) Harmonized Tripartite Guidelines for Good Clinical Practice, with applicable local regulations (including European Directive 2001/20/EC and US Code of Federal Regulations Title 21), and with the ethical principles laid down in the Declaration of Helsinki.

## **11.2 Responsibilities of the investigator and IRB/IEC/REB**

The protocol and the proposed ICF must be reviewed and approved by a properly constituted Institutional Review Board/Independent Ethics Committee/Research Ethics Board (IRB/IEC/REB) before study start. Prior to study start, the investigator is required to sign a protocol signature page confirming his/her agreement to conduct the study in accordance with these documents and all of the instructions and procedures found in this protocol and to give access to all relevant data and records to Novartis monitors, auditors, Novartis Clinical Quality Assurance representatives, designated agents of Novartis, IRBs/IECs/REBs and regulatory authorities as required.

## **11.3 Informed consent procedures**

Eligible patients may only be included in the study after providing written (witnessed, where required by law or regulation), IRB/IEC/REB-approved informed consent.

Informed consent must be obtained before conducting any study-specific procedures (i.e. all of the procedures described in the protocol). The process of obtaining informed consent should be documented in the patient source documents. The date when a subject's Informed Consent was actually obtained will be captured in their CRFs.

Novartis will provide to investigators, in a separate document, a proposed ICF that is considered appropriate for this study and complies with the ICH GCP guideline and regulatory requirements. Any changes to this ICF suggested by the investigator must be agreed to by Novartis before submission to the IRB/IEC/REB, and a copy of the approved version must be provided to the Novartis monitor after IRB/IEC/REB approval.

Women of child bearing potential should be informed that taking the study medication may involve unknown risks to the fetus if pregnancy were to occur during the study and agree that in order to participate in the study they must adhere to the contraception requirement for the

duration of the study. If there is any question that the patient will not reliably comply, they should not be entered in the study.

#### **11.4 Discontinuation of the study**

Novartis reserves the right to discontinue this study under the conditions specified in the clinical study agreement. Specific conditions for terminating the study are outlined in the clinical study agreement.

#### **11.5 Publication of study protocol and results**

Novartis assures that the key design elements of this protocol will be posted in a publicly accessible database such as clinicaltrials.gov. In addition, upon study completion and finalization of the study report the results of this study will be either submitted for publication and/or posted in a publicly accessible database of clinical study results.

#### **11.6 Study documentation, record keeping and retention of documents**

Each participating site will maintain appropriate medical and research records for this trial, in compliance with Section 4.9 of the ICH E6 GCP, and regulatory and institutional requirements for the protection of confidentiality of subjects. As part of participating in a Novartis-sponsored study, each site will permit authorized representatives of the sponsor(s) and regulatory agencies to examine (and when required by applicable law, to copy) clinical records for the purposes of quality assurance reviews, audits and evaluation of the study safety and progress.

Source data are all information, original records of clinical findings, observations, or other activities in a clinical trial necessary for the reconstruction and evaluation of the trial. Examples of these original documents and data records include, but are not limited to, hospital records, clinical and office charts, laboratory notes, memoranda, subjects' diaries or evaluation checklists, pharmacy dispensing records, recorded data from automated instruments, copies or transcriptions certified after verification as being accurate and complete, microfiches, photographic negatives, microfilm or magnetic media, x-rays, and subject files and records kept at the pharmacy, at the laboratories, and medico-technical departments involved in the clinical trial.

Data collection is the responsibility of the clinical trial staff at the site under the supervision of the site PI. The study eCRF is the primary data collection instrument for the study. The investigator should ensure the accuracy, completeness, legibility, and timeliness of the data reported in the eCRFs and all other required reports. Data reported on the eCRF, that are derived from source documents, should be consistent with the source documents or the discrepancies should be explained. All data requested on the eCRF must be recorded. Any missing data must be explained. For eCRFs an audit trail will be maintained by the system.

The investigator/institution should maintain the trial documents as specified in Essential Documents for the Conduct of a Clinical Trial (ICH E6 Section 8) and as required by applicable regulations and/or guidelines. The investigator/institution should take measures to prevent accidental or premature destruction of these documents.

Essential documents (written and electronic) should be retained for a period of not less than fifteen years from the completion of the Clinical Trial unless Sponsor provides written permission to dispose of them or, requires their retention for an additional period of time because of applicable laws, regulations and/or guidelines

## **11.7 Confidentiality of study documents and patient records**

The investigator must ensure anonymity of the patients; patients must not be identified by names in any documents submitted to Novartis. Signed ICFs and patient enrollment log must be kept strictly confidential to enable patient identification at the site.

## **11.8 Audits and inspections**

Source data/documents must be available to inspections by Novartis or designee or Health Authorities.

## **11.9 Financial disclosures**

Financial disclosures should be provided by study personnel who are directly involved in the treatment or evaluation of patients at the site - prior to study start.

# **12 Protocol adherence**

Investigators ascertain they will apply due diligence to avoid protocol deviations. Under no circumstances should the investigator contact Novartis or its agents, if any, monitoring the study to request approval of a protocol deviation, as no authorized deviations are permitted. If the investigator feels a protocol deviation would improve the conduct of the study this must be considered a protocol amendment, and unless such an amendment is agreed upon by Novartis and approved by the IRB/IEC/REB it cannot be implemented. All significant protocol deviations will be recorded and reported in the Clinical Study Report.

## **12.1 Amendments to the protocol**

Any change or addition to the protocol can only be made in a written protocol amendment that must be approved by Novartis, Health Authorities where required, and the IRB/IEC/REB. Only amendments that are required for patient safety may be implemented prior to IRB/IEC/REB approval. Notwithstanding the need for approval of formal protocol amendments, the investigator is expected to take any immediate action required for the safety of any patient included in this study, even if this action represents a deviation from the protocol. In such cases, Novartis should be notified of this action and the IRB/IEC/REB at the study site should be informed according to local regulations (e.g. UK requires the notification of urgent safety measures within 3 days) but not later than 10 working days.

Clinical Development

RAD001, everolimus

Clinical Trial Protocol CRAD001C1X01B / NCT02017860

An open-label, multi-center everolimus roll-over protocol for patients who have completed a previous Novartis-sponsored everolimus study and are judged by the investigator to benefit from continued everolimus treatment

RAP Module 3 – Detailed Statistical Methodology

Author: [REDACTED], Trial Statistician

Document type: RAP Documentation

Document status: Final 1.0

Release date: 20-Apr-2015

Number of pages: 5

Property of Novartis
Confidential

May not be used, divulged, published or otherwise disclosed
without the consent of Novartis

Document History – Changes compared to previous version of RAP module 3.

Version	Date	Changes
1.0	20Apr2015	First version

Table of contents

Table of contents	3
1 Statistical methods planned in the protocol and determination of sample size	4
1.1 Subjects and treatments	4
1.1.1 Analysis sets.....	4
1.1.2 Patient disposition	4
1.1.3 Patient demographics and other baseline characteristics	4
1.1.4 Treatments (study treatment, concomitant therapies, compliance).....	4
1.2 Safety evaluation	5
1.2.1 Adverse events (AEs).....	5
1.3 Determination of sample size	5
2 Clinical Study Report - Appendix 16.1.9 Documentation of statistical methods	5

1 Statistical methods planned in the protocol and determination of sample size

Data will be analyzed by Novartis according to the data analysis section 10 of the study protocol which is available in [Appendix 16.1.1 of the CSR](#). Important information is given in the following sections and details are provided.

Statistical analysis will be performed when all patients discontinued the trial or the 30-day safety follow-up was completed, whichever comes earlier. Those analyses results will be used to document the summary of the safety.

1.1 Subjects and treatments

1.1.1 Analysis sets

Full Analysis Set (FAS): The Full Analysis Set (FAS) comprises all patients who received at least one dose (partial or complete) of everolimus. The FAS will be used for all listings of raw data.

Safety Set: The Safety Set includes all patients who received at least one dose (partial or complete) of everolimus, and have at least one valid post-baseline safety assessment. The statement that a patient had no AEs (on the AEs CRF) constitutes a valid safety assessment.

1.1.2 Patient disposition

The number of patients ongoing at the time of analysis as well as the primary reason for end of treatment will be summarized for FAS.

1.1.3 Patient demographics and other baseline characteristics

Demographic data, like age and gender as well as the parent study number will be summarized descriptively.

Patient demographics and baseline characteristics will be listed by patient.

1.1.4 Treatments (study treatment, concomitant therapies, compliance)

Exposure to everolimus will be summarized for FAS and will be based only on dose administered within this protocol. Study treatment administered during the parent study will not be taken into account.

The following algorithm will be used to calculate the duration of exposure in days:

- Duration of exposure to everolimus (days) = (date of last administration of everolimus) – (date of first administration of everolimus) + 1.

The date of first administration of everolimus is derived as the first date when a nonzero dose of everolimus was administered and recorded on the database of this protocol. The date of last administration of everolimus is defined as is the last date when a nonzero dose of study drug was administered and recorded on the database of this protocol.

The duration of exposure in years is calculated by dividing the duration of exposure in days by 365.25.

The duration includes the periods of temporary interruption.

Everolimus dose administration will be listed by patient.

1.2 Safety evaluation

For all safety analyses, the safety set will be used.

The overall observation period will be divided into two mutually exclusive segments:

1. on-treatment period: from day of first dose of study medication to 30 days after last dose of study medication
2. post-treatment period: starting at day 30 after last dose of study medication.

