## **2 Rationale**

### **2.1 Study rationale and purpose**

The purpose of this study is to collect and assess long-term safety of everolimus in patients who are currently receiving everolimus treatment in a Novartis-sponsored study that has reached its study objectives, are not progressing on the current study treatment as defined by the parent protocol and are unable to access everolimus treatment outside of a clinical study. Parent studies eligible to participate in the roll-over study will be decided by Novartis. Investigator initiated trials (IITs) will not be included. The primary objective of the parent study must have been reached and the parent study must be in the process of being completed and reported.

Patients will continue to receive everolimus until one of the following occurs: no treatment benefit (disease progression) as defined in the parent protocol, unacceptable toxicity develops, consent withdrawal, protocol non-compliance, the investigator feels it is no longer in the patient's best interest to continue therapy, or the patient's death.

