**Table 3-1 Objectives and related endpoints**

Objective	Endpoint	Analysis
Primary To collect and assess long term safety of everolimus	Frequency and nature of AEs	Refer to Section 10.4

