#### **6.4.3 Prohibited concomitant therapy**

Treatment with systemic anticancer agents (chemotherapy, hormone therapy, targeted or biologic agents) other than everolimus is not permitted until disease progression is documented and everolimus is permanently discontinued.

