### **7.1.5 Follow up for safety evaluations**

All patients must be followed up for safety evaluations for 30 days after the last dose of everolimus. At the end of this period, the investigator should contact the patient to inquire about any AE observed during this period. This could be done via a phone contact. Following this there are **no** further follow-up study visits.

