# 8 Safety monitoring and reporting

## 8.1 Adverse events

### 8.1.1 Definitions and reporting

An AE is defined as the appearance of (or worsening of any pre-existing) undesirable sign(s), symptom(s), or medical condition(s) that occur after patient's signed informed consent has been obtained.

Abnormal laboratory values or test results occurring after informed consent constitute AEs only if they induce clinical signs or symptoms, are considered clinically significant, require therapy (e.g., hematologic abnormality that requires transfusion or hematological stem cell support), or require changes in study medication(s).

AEs that begin or worsen after informed consent should be recorded in the AEs eCRF. AE monitoring should be continued for at least 30 days after the last dose of everolimus. AEs (including lab abnormalities that constitute AEs) should be described using a diagnosis whenever possible, rather than individual underlying signs and symptoms. When a clear diagnosis cannot be identified, each sign or symptom should be reported as a separate AE.

AEs will be assessed according to the Common Terminology Criteria for Adverse Event (CTCAE) version 4.03.

If CTCAE grading does not exist for an AE, the severity of mild, moderate, severe, and life-threatening, corresponding to Grades 1 - 4, will be used. CTCAE Grade 5 (death) will not be used in this study; rather, information about deaths will be collected in the End of Treatment eCRF page.

The occurrence of AEs should be sought by non-directive questioning of the patient during the screening process after signing informed consent and at each visit during the study. AEs also may be detected when they are volunteered by the patient during the screening process or between visits, or through physical examination, laboratory test, or other assessments. As far as possible, each AE should be evaluated to determine:

1. The severity grade (CTCAE Grade 1-4)
2. Its duration (Start and end dates or Ongoing at End of Study)
3. Its relationship to the study treatment (Reasonable possibility that AE is related: No, Yes)
4. Action taken with respect to study or investigational treatment (none, dose adjusted/ temporarily interrupted, permanently discontinued, concomitant medication taken, non-drug therapy given, hospitalization)
5. Whether it is serious, where a SAE is defined as in [Section 8.2.1](#)

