1.2.1 Adverse events (AEs)

Summary tables for AEs have to include only AEs that started or worsened during the on-treatment period, the **treatment-emergent** AEs. However, all safety data (including those from the post-treatment periods) will be listed and those collected during the post-treatment period are to be flagged.

The incidence of all treatment-emergent AEs (number and percentage) will be summarized by system organ class (SOC), preferred term, and maximum severity, relation to study treatment.

Deaths reportable as SAEs and non-fatal serious AEs will be listed by patient.

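### AEs that begin after a next anticancer therapy is started within 30 days of the last everolimus dose enter the all-causality treatment-emergent tables unflagged

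*SAP*

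**What the plan says.** The only objective is long-term safety of everolimus, and the only endpoint in Protocol Table 3-1 is "Frequency and nature of AEs".

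Three sets of rules bear on this point.

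- **When another therapy may start.** Protocol 6.4.3 says that systemic anticancer treatment "other than everolimus is not permitted until disease progression is documented and everolimus is permanently discontinued". Once both conditions are met the restriction ends, and no washout is stated. Progression is also the first reason for stopping given in Protocol 2.1: "no treatment benefit (disease progression) as defined in the parent protocol".
- **Which AEs are collected.** Protocol 8.1.1 states that "AE monitoring should be continued for at least 30 days after the last dose of everolimus". Protocol 7.1.5 adds that at the end of the 30 days "the investigator should contact the patient to inquire about any AE observed during this period".
- **Which AEs are tabulated.** SAP 1.2 defines the "on-treatment period: from day of first dose of study medication to 30 days after last dose of study medication", as does Protocol 10.4.1. SAP 1.2.1 then says "Summary tables for AEs have to include only AEs that started or worsened during the on-treatment period", and that incidence is "summarized by system organ class (SOC), preferred term, and maximum severity, relation to study treatment". The one flag planned for the listings is for AEs in the post-treatment period.

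**The concern.** A patient who stops everolimus for progression may begin the next regimen within days. Early toxicity of that regimen would fall inside the everolimus on-treatment window. It would then be counted in the treatment-emergent incidence and maximum-severity tables beside AEs that arose on everolimus. With no control arm, nothing in the study shows how much of the count came from the later drug. At stake is how far the main tables can be read as a description of AEs under everolimus.

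**Working it through.** **There is no planned figure to reproduce.** The documents give no sample size (Protocol 10.5, SAP 1.3), no expected AE rate, and no expected share of patients going on to further therapy. The check is to follow the rules through and then see what can be said about size.

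**Step 1: follow one patient through the rules.** Progression is documented and everolimus is stopped. Protocol 6.4.3 no longer bars another agent. AE collection continues for at least 30 days (Protocol 7.1.5, 8.1.1). An AE that begins after the new agent starts, but by day 30, meets the treatment-emergent definition (Protocol 10.4.1 and 10.4.2; SAP 1.2 and 1.2.1). No rule ends the window at the new therapy, and the post-treatment flag does not reach this AE.

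**Step 2: days of new therapy inside the window.** If the new agent starts on day s after the last dose, and day 30 is counted as on-treatment, the overlap is 30 − s + 1 days:

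| Start day s | Overlap (days) |
|---|---|
| 1 | 30 |
| 7 | 24 |
| 14 | 17 |
| 21 | 10 |
| 28 | 3 |

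**Step 3: share of the window taken by the tail.** For T days on everolimus the share is 30 / (T + 30):

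| Time on everolimus | Calculation | Share |
|---|---|---|
| 90 days | 30 / 120 | 25% |
| 1 year | 30 / 395.25 | 7.6% |
| 2 years | 30 / 760.5 | 3.9% |
| 5 years | 30 / 1856.25 | 1.6% |

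These are shares of time, not of AEs.

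**Step 4: effect on a crude incidence, under assumptions.** None of these inputs is in the documents. Let p be the share of patients who have the event before the window would be cut, q the share of all patients who start a new agent within the 30 days, and r the chance that this agent causes the event before day 30. Assume independence, and ignore other AEs after the cut. A patient counts once, so:

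- planned incidence = 1 − (1 − p)(1 − q·r)
- rise over the cut window = (1 − p)·q·r

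Results:

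- p = 20%, q = r = 10%: 0.80 × 0.01 = 0.8 points, the smallest rise on the grid p = 5–20%, q = 10–50%, r = 10–50%.
- p = 10%, q = r = 30%: 0.90 × 0.09 = 8.1 points, so 10% becomes 18.1%.
- p = 5%, q = r = 50%: 0.95 × 0.25 = 23.75 points, the largest rise on the grid.
- q = 0: no change.

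The factor (1 − p) matters. A patient who already had a grade 3-4 AE adds nothing to the overall grade 3-4 count by having another. The width of the range shows that the size is unknown; it is not an estimate.

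**The case against.** The case on the other side is substantial.

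- **Treatment-emergent is a timing class, not a causal claim.** Causality is handled separately. The investigator judges each AE's relationship to study treatment (Protocol 8.1.1), and the tables are split by it (SAP 1.2.1). Under Protocol 6.1 study treatment already includes parent-study combination drugs, so the all-causality tables were never about everolimus alone. This stands as a limit on what may be claimed. It does not remove the point: relatedness is an open-label yes/no judgement, and it leaves the all-causality tables unchanged.
- **Few patients may be affected.** Entrants are benefiting from everolimus, and the study may stay open for 5 years, so long exposures with a small tail are plausible. The programme also covers tuberous sclerosis indications, where a next anticancer therapy may not apply. This stands, and the documents cannot settle it.
- **The listings already help.** The date and reason for stopping are in the eCRF (Protocol 7.1.4), and AE start dates are recorded. A reader can find AEs that began after the last dose in patients who stopped for progression. That narrows the field, but does not show whether or when a new agent was started.
- **The start date may already be collected.** The body of Table 7-1 could not be read in the available copy, and the eCRF is not among the documents. This stands: no readable text asks for the date, but its absence cannot be asserted.
- **The study is descriptive.** No test or comparison depends on these counts. This limits the consequence, but AE frequency is still the only endpoint.

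**Conclusion.** The point holds as a cheap improvement to the plan. As written, AEs that start or worsen after a next systemic therapy begins, within 30 days of the last everolimus dose, enter the all-causality incidence and maximum-severity tables and cannot be told apart there. Against a window cut at new therapy, the effect can only be upward. Its size rests on how many patients start new therapy in the tail and how toxic that therapy is, and the documents give neither.

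A reader might infer more than this, and the documents do not support it:

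- that the plan attributes these AEs to everolimus. It reports relatedness separately;
- that every AE in the 30 days is counted. Only AEs that start or worsen in the window are, so an unchanged ongoing AE is not counted again;
- that the 25% figure is typical. It needs a patient to stop after 90 days, and it measures time;
- that a particular percentage of patients gains a grade 3-4 AE from another drug. Any such figure needs assumed inputs and must allow for patients who already had one;
- that the start of new therapy is not recorded. This cannot be known from the available text.

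**What to change.** 1. If the eCRF does not already hold it, record the start date of any new systemic anticancer therapy up to the day-30 contact.
2. In SAP 1.2, keep the 30-day window as the main definition.
3. In SAP 1.2.1, flag in the listings every AE with onset or worsening on or after that date.
4. Repeat the overall and grade 3-4 AE tables with the on-treatment period ending at the earlier of 30 days after the last dose or the day before new therapy. For patients with no new therapy the window is unchanged.

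The cost is at most one date field and one question at an existing contact, plus one flag and two repeat tables. If the date is already collected, only the SAP changes. If it is not, adding the question may need a minor amendment under Protocol 12.1.

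The downside is that some delayed everolimus AEs drop out of the repeat tables, though they stay in the main ones. The difference between the two sets should therefore be read as AEs arising after new therapy began, not as AEs caused by it. No clinical rule changes.

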### **7.1.1 Enroll visit**

There will be no screening period for this study. At the enrollment visit, the patient will need to complete a written informed consent. Once consented, patients will be evaluated for eligibility via the inclusion and exclusion criteria.

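### Adverse events starting between roll-over consent and the first roll-over dose belong to no analysis segment, so they drop out of the summary tables and are unflagged in the listings

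*SAP*

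**What the plan says.** Protocol 8.1.1 sets the start of collection: "AEs that begin or worsen after informed consent should be recorded in the AEs eCRF". It also asks for active enquiry before dosing: "The occurrence of AEs should be sought by non-directive questioning of the patient during the screening process after signing informed consent". SAE reporting likewise starts at consent (Protocol 8.2.2).

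For analysis, Protocol 10.4.1 states: "The overall observation period will be divided into two mutually exclusive segments". SAP 1.2 uses the same split. The first segment is the "on-treatment period: from day of first dose of study medication to 30 days after last dose of study medication" and the second is the "post-treatment period: starting at day 30 after last dose of study medication". Neither document defines a segment before the first dose.

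The tabulation rule is in SAP 1.2.1, and Protocol 10.4.2 agrees with it: "Summary tables for AEs have to include only AEs that started or worsened during the on-treatment period". All safety data are listed, but only post-treatment data are flagged.

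For exposure, SAP 1.1.4 dates first administration as the "first date when a nonzero dose of everolimus was administered and recorded on the database of this protocol" and leaves out dosing in the parent study. SAP 1.2 does not say whether its own first dose carries the same meaning.

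**The concern.** The two segments are presented as a division of the whole observation period, yet they do not reach back to where AE collection begins. An event in the uncovered interval is collected and then has no place in the analysis.

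In a drug-naive population this would matter little, because an event before the first dose cannot be due to the drug. Here inclusion criterion 1 (Protocol 5.2) requires the patient to be receiving everolimus already, exclusion criterion 1 (5.3) removes those permanently taken off it, and the starting dose equals the last parent-study dose (6.1.1). The interval is therefore normally time on drug. The only endpoint is the frequency and nature of AEs (Table 3-1), and leaving these events out of the tables can only lower the tabulated counts.

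**Working it through.** The plan gives no figure on this point, so there is none to reproduce. The check is to apply the segment rule to every possible onset day and then to size the result under stated assumptions.

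**Does an interval exist?** Consent comes first: "Once consented, patients will be evaluated for eligibility via the inclusion and exclusion criteria" (Protocol 7.1.1). Women of child-bearing potential also need a locally done serum pregnancy test at enrollment (7.2.2). Dosing follows as soon as the patient is consented and eligible (2.2). No maximum interval is stated, so the gap may be zero but is not fixed at zero.

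**Which days are uncovered?** Let day 0 be consent, day g the first roll-over dose and day L the last dose.

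- On-treatment: g ≤ t ≤ L + 30
- Post-treatment: t ≥ L + 30
- Neither: 0 ≤ t ≤ g − 1, which is exactly g days

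So g = 0, 1, 7, 14 or 28 leaves 0, 1, 7, 14 or 28 onset days unassigned. Same-day dosing loses nothing, because the on-treatment period includes the whole day of first dose. (Day L + 30 meets both conditions. That overlap is a separate matter.)

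**What happens to an AE with onset on an uncovered day?**

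- Summary tables: excluded, unless it worsens on or after day g, since the rule admits events that started or worsened on treatment.
- Listings: included, with no flag.
- Deaths reportable as SAEs and non-fatal SAEs: listed by patient.

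**How large is the interval relative to follow-up?** Share = g / (g + D + 30), where D is days of treatment: 91, 365 and 1,826 for 3 months, 1 year and 5 years. The values of g and D are assumptions, except that 5 years is the period for which the study is expected to stay open. For example, g = 7 and D = 365 gives 7 / 402 = 1.74%.

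| Gap g (days) | 3 months | 1 year | 5 years |
|---|---|---|---|
| 0 | 0% | 0% | 0% |
| 1 | 0.82% | 0.25% | 0.05% |
| 7 | 5.47% | 1.74% | 0.38% |
| 14 | 10.37% | 3.42% | 0.75% |
| 28 | 18.79% | 6.62% | 1.49% |

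**What might that mean in events?** Assume 50 patients and 2 to 5 AEs per patient-year; neither figure is in the documents. Expected events in the gap = 50 × rate × g / 365.25:

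- g = 1: 0.3 to 0.7
- g = 7: 1.9 to 4.8
- g = 14: 3.8 to 9.6

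Over one year the same patients would have 50 × 2 = 100 to 50 × 5 = 250 events, so even a 14-day gap holds about 14 / 365.25 = 3.8% of a year's events.

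**The case against.** The strongest reply is that the design makes the interval close to zero. There is no screening period, and patients may start everolimus as soon as they enter (Protocol 4.1). A local pregnancy test need not take days. The body of Table 7-1, which might place enrollment and first dose at one visit, was not in the text available for review. This stands as an argument about size: the 7-, 14- and 28-day cases are illustrations, not findings. It does not close the gap in the definition, because no maximum interval is set.

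A reader might infer that these AEs are lost, or that the plan treats them as off-treatment events. The documents do not support either reading. The events remain in the listings, serious ones are listed by patient, and those that worsen after the first dose are tabulated. Only post-treatment data are flagged, so nothing labels the gap events as off treatment.

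The event counts above also overstate the effect on the planned tables. SAP 1.2.1 reports incidence as number and percentage. If patients are counted once per preferred term, an event that recurs after the first dose is captured anyway.

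Two further limits stand. First, reading first dose as the first roll-over dose borrows a definition that SAP 1.1.4 writes for exposure. Second, that patients are on drug throughout the interval is inferred from their status at entry; a temporary interruption at transfer would be an exception. Parent-study reporting might also capture these events, but the documents do not say so.

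It is tempting to conclude that the on-treatment period should simply start at consent. That would put the AE window out of line with exposure, which SAP 1.1.4 counts only from dosing under this protocol. Limiting it to patients without a treatment break would require parent-study dosing dates, which neither document describes as collected.

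**Conclusion.** The point holds as a gap in definition. The stated two-segment split does not cover the period over which AEs are collected, and an AE that starts between consent and the first roll-over dose is untabulated unless it worsens, and unflagged. Any effect on the tables is towards fewer AEs. It is nil with same-day consent and dosing and probably small otherwise. A reader might infer a material undercount of the endpoint; the documents do not show one, because they give no interval, sample size or AE rate. The conclusion rests on first dose meaning the first dose in this protocol. If the sponsor means something else, SAP 1.2 needs to say so.

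**What to change.** In Protocol 10.4.1 and SAP 1.2:

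1. State that first dose means the first everolimus dose recorded in this protocol's database.
2. Add a third segment, from the date of informed consent to the day before that dose. It is empty when the two dates coincide.
3. In a separate row or small table, report the number and percentage of patients with AEs and with SAEs starting in that segment, and flag those events in the listings. The row counts by onset, so an event that later worsens also stays in the treatment-emergent tables; a footnote should say that the two are not to be added.

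Leave the exposure definition and the treatment-emergent window unchanged, so that AE and exposure windows stay aligned.

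No new data are needed. The consent date (Protocol 11.3), dosing records (6.6) and AEs from consent (8.1.1) are already captured. The cost is a short wording change in each document, one small extra table and a flag.
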